Primary Efficacy Endpoint	The primary efficacy endpoint is the percent of subjects with $\geq 15$ letters of improvement in photopic binocular DCNVA and with < 5 letters of loss in photopic binocular BCDVA at 30 min post-LDP/vehicle comparing Nyxol + LDP to placebo + LDP vehicle at Visit 5 (Stage 2 Day 8). This comparison will be analyzed first using a hierarchical testing method.
Key Secondary Efficacy Endpoints	
Other Secondary Efficacy Endpoints	

09/29/2023 Page 11 of 76

	All efficacy endpoints will be analyzed overall and by light/dark irides. Separate analyses will be performed for binocular, study eye, and fellow eye, where applicable. All efficacy endpoints will also be analyzed by the Modified Intention-to-Treat (mITT) Population. Selected analyses will be performed on the Per Protocol (PP) Population as specified in the Statistical Analysis Plan (SAP).
Safety Endpoints	Safety measures are adverse events, ocular tolerability, IOP, BCDVA, biomicroscopy, ophthalmoscopy, HR and BP, and subject questionnaire. Urine pregnancy tests for females of childbearing potential will be conducted.
Study Medications, Dose, and Mode of Administration	Treatment 1:         • Nyxol ® Eye Drops (Phentolamine Ophthalmic Solution 0.75%), or         • Placebo (ie, Nyxol vehicle)         Treatment 1 is dosed during both Stages 1 and 2 of the study and is taken daily in the evenings near bedtime, except during the Washout Period.         Treatment 2:         • LDP (Pilocarpine Hydrochloride Ophthalmic Solution 0.4%), or         • LDP vehicle         Treatment 2 is dosed during Stage 2 of the study and is taken daily in the mornings.

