## 3.1. Findings From Nonclinical and Clinical Studies

# Nyxol

Detailed findings from nonclinical and clinical studies for phentolamine mesylate or phentolamine ophthalmic solutions and potential risks are provided in the Investigators' Brochure (IB) (2022).

Nyxol has been studied in a total of 12 clinical trials (three Phase 1, five Phase 2, and four Phase 3) enrolling over 1100 subjects (including subjects 3 years of age and up, with over 650 subjects treated with Nyxol) and has demonstrated promising clinical data for use in multiple ophthalmic indications.

In prior clinical trials, Nyxol has demonstrated a consistent ability to decrease pupil diameter (PD) by approximately 20% - 30% (~1-1.5 mm) in both mesopic and photopic conditions (1-3). Nyxol has been found to be efficacious for more than 24 hours, with an onset of action of approximately 30 to 60 min. Nyxol has been observed to be well tolerated at single doses and multiple doses up to 14 days. Safety of the subjects in these trials was evaluated by adverse event (AE) monitoring, physical examinations, and vital sign assessments. Across all trials, no serious adverse events (SAEs) have been reported. No deaths occurred in any of the trials. No clinically meaningful changes were observed in physical examinations or vital signs, including blood pressure (BP) and heart rate (HR). Adverse events reported were mild to moderate in intensity, with the most common being transient conjunctival hyperemia (eye redness) and ocular irritation; however, Nyxol dosing at or near bedtime was observed to mitigate or minimize these side effects during the daytime.

The VEGA-1 study evaluated the efficacy and safety of Nyxol in combination with LDP and as a single agent in presbyopic subjects. The study met its primary and many secondary endpoints.

Nyxol + LDP showed a favorable safety profile with no serious AEs. Most AEs were mild, with no headaches, no browaches, and no blurry vision AEs reported. Mild, transient conjunctival hyperemia AEs were reported in < 5% of subjects.

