# 5. STUDY DESIGN

This is a randomized, double-masked, placebo-controlled, multicenter, Phase 3 study in approximately 320 subjects with presbyopia. The study will be performed in 2 stages, as shown in Appendix 4.

Subjects will be randomized 1:1:1:1 to treatments for both stages at Visit 1 (Screening/Baseline). Treatment 1 assignment in Stage 1 will be maintained for Stage 2. Stage 1 will consist of 2 treatment groups (Nyxol or placebo [ie, Nyxol vehicle]), with approximately 160 subjects in each group. Stage 2 consists of 4 treatment groups (Nyxol + LDP, Nyxol + LDP vehicle, placebo + LDP, and placebo + LDP vehicle), with approximately 80 subjects per treatment group.

In Stage 1, the safety and efficacy of Nyxol as a single agent will be evaluated over the following 1 day and 7 days of daily dosing in the evenings near bedtime, except the evening before Visit 2, when Treatment 1 is dosed as close to 12 hours prior to Time 0 min for that visit. Following Visit 2 (Stage 1 Day 8), subjects will discontinue dosing Treatment 1 for 7 to 14 days (Washout Period). During the Washout Period, subjects will return for Visit 3 (Stage 1 Day  $10 \pm 1$  day) to assess the resolution of drug treatment effects.

During Stage 1, subjects will dose with Treatment 1 (Nyxol or placebo [ie, Nyxol vehicle]) in the evenings near bedtime (except for Visit 1 [Stage 1 Day 1], when the subject is dosed during the day at the study site).

Measurements will be made at multiple visits and timepoints, and analysis will consist of comparison across the 2 arms:

- Nyxol
- Placebo

# Stage 2: Dosing of Treatments 1 and 2

Visit 4 (Stage 2 Day 1) is the start of Stage 2. In Stage 2, the efficacy and safety of Nyxol + LDP will be evaluated following 1 day and 7 days of dosing, in which Treatment 1 (Nyxol or placebo) is dosed daily in the evenings near bedtime, except the evening before Visits 4 and 5, when Treatment 1 is dosed as close to 12 hours prior to the scheduled time for those visits. Treatment 2 (LDP or LDP vehicle) is dosed daily in the mornings. Treatment 2 will be dosed at the study site at the beginning of Visits 4 and 5 (Stage 2 Days 1 and 8, respectively).

Measurements will be made at multiple visits and timepoints, and analysis will consist of comparison across the 4 arms:

- Nyxol + LDP
- Nyxol + LDP vehicle
- Placebo + LDP
- Placebo + LDP vehicle

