#### Ocuphire Pharma, Inc. OPI-NYXP-301

assessments are recommended to be performed on the same day; however, in instances in which subjects are unable to complete the full day of assessments for Visit 1, subjects may be scheduled to return for the completion of Visit 1 within 1 week of Screening. If Visit 1 is split over 2 separate days, all Screening assessments up to and including randomization must occur on the first day, and then the subject should return to complete their post-randomization assessments on the second day. \*Postrandomization assessments to be performed on the second day (ie, confirm concomitant medications, subject questionnaire, in-office Treatment 1 dosing, ocular tolerability, followed by all other assessments at time points 0.5, 1, 3, 5, and 8 hours post-treatment).

[b] Time of visits will be scheduled relative to the prior evening's dose of Treatment 1. Visit 2 will be scheduled such that the 0 hour (Time 0 min) assessments on Visit 2 will occur approximately 12 hours ( $\pm 1$  hour) after the prior evening's dose of Treatment 1. Visit 3 occurs at Stage 1 Day 10 ( $\pm 1$  day) during the Washout Period. [c] An additional  $\pm 5$  min is permitted for measurements at 0.5 and 1 hour; an additional  $\pm 10$  min is permitted at 3, 5, and 8 hours for Visits 1 and 2.

[d] Urine pregnancy test is for females of childbearing potential only.

[h] IOP performed with Tono-Pen or Goldmann applanation tonometry.

[i] Direct or indirect ophthalmoscopy performed without dilation. Use of 90 D lens (indirect) is allowed.

[j] Treatment 1: At Visit 1 (either first or second day of Visit 1, see \* above), one drop of Nyxol or placebo (ie, Nyxol vehicle) will be dosed at the study site after the completion of 0 hour (Time 0 min) ocular assessments. Subject will dose with Treatment 1 each evening near bedtime, starting the evening of Stage 1 Day 2 through the evening prior to Visit 2 (Stage 1 Day 8), except the evening before Visit 2, when Treatment 1 is dosed as close to 12 hours prior to Time 0 min for that visit. Subjects will discontinue dosing during the 7- to 14-day Washout Period.

[k] Ocular tolerability performed it will be assessed at the beginning of each specified timepoint after dosing at Visits 1 and 2.

[1] Subject guestionnaire (Appendix 5 and Appendix 6) will be completed by the subject at specified visits and timepoints.

Table 2:Schedule of Events for Stage 2

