At Visit 1 (Stage 1 Day 1), eligible subjects will be randomized, and the first dose of Treatment 1 will be administered at the study site at Time 0 min. Efficacy and safety measurements are made before dosing with Treatment 1 (Time 0 min) and at multiple post-dose timepoints from 30 min to 8 hours. If Visit 1 is split over 2 separate days, all Screening assessments up to and including randomization must occur on the first day, and then the subject should return to complete their post-randomization assessments in the following order on the second day (ie, confirm concomitant medications, subject questionnaire, in-office Treatment 1 dosing, ocular tolerability, followed by all other assessments at time points 0.5, 1, 3, 5, and 8 hours post-treatment). The following assessments are conducted during Visit 1:

Prior/Concomitant medication

Heart rate and BP

Pupil diameter (photopic and mesopic)

Distance-corrected near VA BCDVA
DCIVA ); all VA measurements will be made , except selected
measurements at 0 min ), which will
be measured binocularly followed by OD and OS measurements
Biomicroscopy
Intraocular pressure
Ophthalmoscopy
Ocular tolerability
Subject questionnaire

Adverse events

Treatment 1/Diary dispensing

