- Drug withdrawn: An indication that a medication schedule was modified through termination of a prescribed regimen of medication
- Not applicable: Determination of a value is not relevant in the current context
- Unknown: Not known, not observed, not recorded, or refused

Additional other action taken:

- Concomitant medication
- Hospitalization

Outcome of an AE is coded as:

- Fatal: The termination of life as a result of an AE
- Not recovered/not resolved: One of the possible results of an AE outcome that indicates that the event has not improved or the subject has not recuperated
- Recovered/resolved: One of the possible results of an AE outcome that indicates that the event has improved or the subject has recuperated

- Recovered/resolved with sequelae: One of the possible results of an AE outcome where the subject recuperated but retained pathological conditions resulting from the prior disease or injury
- Recovering/resolving: One of the possible results of an AE outcome that indicates that the event is improving
- Unknown: Not known, not observed, not recorded, or refused

In previous clinical studies of Nyxol, the most frequently reported AE was conjunctival hyperemia. Investigators are cautioned to use the appropriate verbatim term on the AE form to describe this observation:

- Redness related to instillation that is transient (ie, is no longer present 2 hours after instillation) = "conjunctival erythema upon instillation"
- Redness that is NOT transient (ie, is present 2 hours after instillation) = "conjunctival hyperemia"

**Expedited reporting of serious and unexpected adverse** events: All SAEs (related and unrelated) will be recorded following subject signature of the ICF consent and until the completion of Visit 5. Any SAEs "suspected" to be related to the study medication and discovered by the Investigator at any time **after** the study must be reported.

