### **10.1. Adverse Events**

AEs will be coded using MedDRA, Version 25.1.

Treatment-emergent adverse events (TEAEs) are defined as any AE that begins or worsens after initiation of the investigational product and through the subject's last study visit (study completion or early termination).

If the onset of an AE is on or after the date of first dose of study medication or is increasing in severity after first dose of study medication, then the AE will be considered treatment emergent.

Only TEAEs will be summarized; all AEs (TEAE, non-TEAE) will be included in a by-subject listing.

TEAEs that start during Stage 1 will only be counted in the Stage 1 tables using the Treatment 1 that was actually taken, regardless of the TEAE stop date. TEAEs that start during Stage 2 will be counted in both Stage 1 and Stage 2 tables.

The number and percent of subjects with any TEAEs will be summarized by SOC and PT by treatment group and overall. At each level of tabulation (e.g., at the PT level), subjects will be counted only once if they had more than one such event reported during the AE collection period.

Note that in MedDRA, ocular events are coded to the SOC of "Eye Disorders". Thus, using SOC in the summaries will provide a separation of ocular and non-ocular adverse events.

The following summary tables will be presented for TEAE data:

- Overall summary of TEAEs (completed for both the SP and mITT population)
- Summary table of TEAEs by SOC and PT
- Summary table of TEAEs by SOC, PT, and by greatest relationship level to study drug (not related, unlikely related, possibly related, probably related, definitely related, or unknown)
- Summary table of TEAEs by SOC, PT, and maximum severity (mild, moderate, severe)

- Summary table of serious TEAEs by SOC and PT
- Summary table of TEAEs leading to withdrawal from the study by SOC and PT
  
- Summary table of TEAEs leading to study medication discontinuation by SOC and PT

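### Eye redness is split into two adverse event terms by its state 2 hours after the drop, which will usually go unobserved for evening doses, and no pooled redness count is visibly planned

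*Protocol*

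**What the plan says.** Protocol 9.3.1 notes that conjunctival hyperemia was the most frequent adverse event in earlier Nyxol studies and tells investigators which verbatim term to enter:

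- When the eye is still red at the cut-off, the entry is: "Redness that is NOT transient (ie, is present 2 hours after instillation) = 'conjunctival hyperemia"
- When the eye has cleared before the cut-off, the entry is: "Redness related to instillation that is transient (ie, is no longer present 2 hours after instillation) = 'conjunctival erythema upon instillation"

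The section does not say what to enter when nobody saw the eye at 2 hours.

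Treatment 1 (Nyxol or its placebo), according to the Protocol synopsis, "is taken daily in the evenings near bedtime, except during the Washout Period". The exception is Visit 1, "when the subject is dosed during the day at the study site".

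SAP 10.1 plans the main adverse event table as follows: "The number and percent of subjects with any TEAEs will be summarized by SOC and PT by treatment group and overall". A subject counts once within each preferred term. The visible list of TEAE tables contains no combined redness count. The full list of planned tables (SAP 12.1) is blacked out.

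Protocol 3.1 describes the earlier Phase 2 result for Nyxol + LDP in these words: "Mild, transient conjunctival hyperemia AEs were reported in < 5% of subjects".

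**The concern.** Adverse events are one of the two primary safety measures (Protocol 9.1), and redness is the event this product is best known for. The two terms differ only in the state of the eye at 2 hours. After a drop near bedtime, that moment will often fall during sleep. Events are sought mainly by an open question at the next visit (Protocol 9.3.1), which can be several days later. The documentation listed in Protocol 9.3 includes start and end dates; times are mentioned only for a change in severity. The choice of term may therefore be a guess that cannot be checked afterwards.

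If the tables then follow the two terms, a reader who takes the hyperemia row as the redness rate will read a figure that is too low, by an amount that depends on filing habits. The word itself also shifts within the Protocol. Section 3.1 speaks of transient hyperemia, while section 9.3.1 reserves hyperemia for redness that is not transient. A lower hyperemia rate in this trial could come from the labelling alone.

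**Working it through.** The plan gives no redness rate to reproduce. The check has three parts: count the doses, see when the eye is looked at, and work through what the split does to the tabulated rate.

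**1. Dosing occasions, on the scheduled days**

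- Treatment 1, Visit 1, by day at the site: 1.
- Treatment 1, Stage 1 at home, "starting the evening of Stage 1 Day 2 through the evening prior to Visit 2" (Stage 1 Day 8): evenings of Days 2 to 7 = 6.
- Treatment 1, Stage 2 at home (Protocol 3.5): the evening before Visit 4, then the evenings of Stage 2 Days 1 to 7 = 1 + 7 = 8.
- Treatment 1 total: 1 + 6 + 8 = 15, of which 6 + 8 = 14 (93%) are at home in the evening. Three of these are timed about 12 hours before Visits 2, 4 and 5, which leaves 11 at ordinary bedtime.
- Treatment 2 (Protocol 5.2, Table 2 footnotes): 8 morning doses, 2 of them at the site (Visits 4 and 5).
- Both treatments: 15 + 8 = 23 occasions, of which 1 + 8 = 9 (39%) are by day and 1 + 2 = 3 are at the site.

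**2. When the eye is looked at**

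- After the Visit 1 dose, the drop and tolerability rating are "followed by all other assessments at time points 0.5, 1, 3, 5, and 8 hours post-treatment". Visits 4 and 5 use the same times after Treatment 2. So 1 hour and 3 hours bracket the cut-off for the 3 site doses, but no dose of either treatment has a scheduled 2-hour assessment.
- SAP 10.7 summarizes biomicroscopy at baseline, at Visit 2 (12 hours after Treatment 1) and at Visit 5 (8 hours after Treatment 2, so about 12 + 8 = 20 hours after Treatment 1).
- Redness still there on waking or at the 12-hour examination points to the non-transient term. Redness that was noticed after the drop and had gone by morning cannot be placed.

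**3. Effect on the tabulated rate, if the terms code to two preferred terms**

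Let R be the share of subjects with any reported redness, s the share of those still red at 2 hours, and m the share of the latter filed as transient because the 2-hour state was not seen. Put each subject in one term only:

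- hyperemia row = R × s × (1 − m)
- instillation row = R − hyperemia row
- pooled row = R, whatever s and m are

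The documents give none of R, s or m, so these values are assumptions. With R = 10% and s = 50%:

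| m | Hyperemia row | Instillation row | Pooled |
|---|---|---|---|
| 0 | 10% × 0.5 × 1 = 5.0% | 5.0% | 10% |
| 0.5 | 10% × 0.5 × 0.5 = 2.5% | 7.5% | 10% |
| 1 | 10% × 0.5 × 0 = 0% | 10% | 10% |

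Over R = 5% to 20%, s = 25% to 75% and m = 0 to 1, the hyperemia row runs from 0% to 20% × 0.75 = 15%.

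In practice a subject can have one term after one dose and the other term after another, so adding the rows does not give R either. If the rows read 10% and 8% (assumed), the share with any redness lies between 10% (full overlap) and 18% (no overlap). It is 1 − 0.90 × 0.92 = 17.2% if the two are independent.

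**The case against.** A reader might infer more than this, and the documents stop short of it in five respects.

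- **That the 2-hour state cannot be observed.** Sleep at 2 hours is an inference. Three evening doses are timed to a visit, persistent redness can be classified on waking or at the 12-hour examination, and the rule also covers Treatment 2, which is dosed in the morning. *Usually not observed, for most Treatment 1 doses* is as far as the text goes.
- **That the redness rate is lost.** Both terms are collected, and SAP 10.1 puts every adverse event in a by-subject listing. Anyone with the data can count subjects with either term. Redness that comes and goes unseen during sleep would be missed under any wording; dosing time and passive collection cause that, not the split.
- **That the tables will certainly show two rows.** The Protocol prescribes verbatim terms, while the SAP tabulates preferred terms. The mapping is not stated. If both verbatims code to one preferred term, the planned table already pools them and counts each subject once. A pooled row could also be in the blacked-out list of planned tables.
- **That the comparison with placebo becomes uninterpretable.** The same rule applies in every arm under masking. Uncertain filing blurs the two terms, but arms can still be compared on each term or on both together.
- **That the earlier rate of less than 5% was counted under a different rule.** Protocol 3.1 does not define transient, the naming rule used in that study is not given, and no visible text plans a formal comparison. The two rates may not be comparable; the documents do not show that they are not.

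All five limits stand. They leave untouched that the Protocol has no rule for the unseen case, that the mapping is unstated, and that no pooled count is pre-specified in the visible text.

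**Conclusion.** The point holds in a limited form. For 14 of 15 Treatment 1 doses, redness must be named by a 2-hour state that will usually not have been observed, and the Protocol does not say how to file it. If the verbatims code to different preferred terms, the TEAE tables split the best-known side effect by an unreliable label. The hyperemia row alone then understates reported redness whenever some subjects carry only the instillation term, and it may not be comparable with the rate quoted in Protocol 3.1.

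The size depends on rates that the documents do not give. In the example the row can read anywhere from 5.0% down to 0% against a pooled 10%. The conclusion rests on three assumptions: separate preferred terms, no pooled row in the blacked-out table list, and evening doses taken as scheduled. The reported total stays recoverable from the listings and the between-arm comparison stays possible. This is a cheap improvement to the reporting and does not put the safety analysis as a whole in doubt.

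**What to change.** - **SAP 10.1:** pre-specify a row for any conjunctival redness that counts each subject once if either term was reported, by treatment group, severity and relationship, with the two terms as sub-rows. Name it as the redness rate to be reported.
- **SAP 10.1 or 7.3.5:** state the preferred term to which each of the two verbatims is coded.
- **Protocol 9.3.1:** state how redness is recorded when its 2-hour state was not observed. Restricting the split to doses given in the clinic would not do, because redness after home doses, nearly all of the Treatment 1 exposure, would then have no assigned term.

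The cost is one extra row per TEAE table, a line on coding and a sentence in the Protocol. The SAP changes need no new data; the recording rule helps only for events entered after it takes effect. The stated redness rate may look less favourable than the hyperemia row alone.

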#### 9.3.2. Follow-Up of Subjects After Adverse Events

If an AE/adverse reaction occurs, the Investigator will institute support and/or treatment as deemed appropriate. All SAEs ongoing at the time of the last visit or discontinuation from the study will be followed up until the AE/adverse reaction is resolved or stabilized, the subject is lost to follow-up, or there is other resolution to the event.

## **10. STATISTICS**

#### 10.1. Sample Size

Subjects will be randomized 1:1:1:1 to Nyxol + LDP, Nyxol + LDP vehicle, Placebo + LDP, and Placebo + LDP vehicle respectively. As a result, subjects will be randomized 1:1 to Treatment 1 (Nyxol or placebo).

An additional 20 subjects will be enrolled to account for dropouts, for a total of approximately 320 subjects to be randomized.

A diagram outlining the study design can be found in Appendix 4.

#### 10.2. Analysis Populations

**Modified Intention-to-Treat Population:** The mITT Population will include all randomized subjects who received at least 1 drop of Treatment 1. The mITT Population will be used to analyze the primary endpoint as well as other efficacy endpoints.

**Per Protocol Stage 1 Population:** The PP Stage 1 (PPS1) Population will include all subjects in the mITT Population who receive 1 drop of Treatment 1 the day prior to Visit 2, have binocular DCNVA and BCDVA in photopic conditions at Baseline (Visit 1) and at 12 hours post-dose at Visit 2, and have no major protocol deviations considered to have significant impact on treatment outcome in Stage 1. The PPS1 Population will be used for analysis of select efficacy endpoints as specified in the SAP.

**Per Protocol Stage 2 Population:** The PP Stage 2 (PPS2) Population will include all subjects in the PPS1 Population who receive 1 drop of Treatment 1 the day prior to Visit 4, receive 1 drop of Treatment 2 at Visit 4, have binocular DCNVA and BCDVA in photopic conditions for at least 1 timepoint at Visit 4 after Treatment 2 dosing, and have no major protocol deviations considered to have significant impact on treatment outcome in Stage 2. The PPS2 Population will be used for analysis of select efficacy endpoints as specified in the SAP.

**All Randomized Population (ARP):** The ARP will include all randomized subjects. This population is also known as the Intention-to-Treat (ITT) Population. The ARP will be used in confirmatory efficacy analyses.

**Safety Population (SP):** The SP will include all randomized subjects who have received at least 1 drop of study treatment (Treatment 1 or Treatment 2). The SP will be used to summarize safety variables.

Per Protocol Populations include PPS1 and PPS2 throughout this document.

